1 STUDY DESIGN

This research will examine the initial feasibility and acceptability of a values-affirmation, education, and skills-training intervention targeting HF medication adherence using the NIH Stage Model for Behavioral Intervention Development (Onken et al., 2014). Older adults with HF will be invited to engage in a values-affirming exercise and review tailored medication education and skills-training with a study interventionist. Participants will use a pillbox with electronic monitoring capabilities with a personalized value label as a reminder of their core values throughout the study.

Design: This study is a Stage 1B (NIA Stage Model) trial and will use a single-arm design. No randomization or participant blinding will occur.

Setting: Study assessments and intervention delivery will occur either at the participant's home or The Miriam Hospital's Center for Behavioral and Preventive Medicine (CBPM). The location will be determined by participant preference. Data management and analysis will be housed at CBPM.

Study Duration: Study duration is estimated to be 9-12 months from the time of enrollment of the first subject to completion of data cleaning and analysis. Each individual participant will complete the protocol within 4 weeks from the time of the baseline visit until the end-of-treatment assessment.

Sample: 12 older men and women with HF, ages 55 and older, who are within the first monthof a CR program in Providence, Rhode Island will be recruited. We aim to recruit a sample that is 50% women and 15% individuals who identify as a member of a racial or ethnic minority identity.

2 PRIMARY OBJECTIVE

This study reflects one of a series of studies designed to develop and test a values affirmation medication adherence intervention for older adults with heart failure (HF). The primary objectives are to assess intervention feasibility and acceptability through a small open, singlearm trial. Primary endpoints are feasibility of recruitment procedures, feasibility of intervention procedures, and acceptability. We hypothesize that the intervention will be 1) feasible, and 2) acceptable.

Note. Administration of assessment measures are for feasibility evaluation only.

3 SELECTION AND ENROLLMENT OF PARTICIPANTS

3.1 Inclusion Criteria

Older adults with a diagnosis of HF upon admission and other CR participants within the first month of enrollment with a HF diagnosis regardless of CR referral reason will be eligible for inclusion. Only HF patients who are indicated as being at risk of medication-non adherence will be eligible (i.e., as indicated by a referral to the CR pharmacy consultation service OR based on medication adherence screening measures OR if they are prescribed ten or more medications).

Additional inclusion criteria will include: (1) adults \geq the age of 55 at the time of CR initiation and (2) English-speaking.

3.2 Exclusion Criteria

(1) current participation in a medication-monitoring clinical or research protocol, (2) severe cognitive impairment on cognitive screening measures or diagnosis of Alzheimer's or dementia, (3) current suicidality, (4) acute psychosis, (5) chart documentation of NYHA-class IV HF, (6) terminal illness with an expected lifespan of less than six months, or (7) patient report that someone other than the patient is primarily responsible for the patient's medication management and medication-taking.

3.3 Study Enrollment Procedures

Recruitment

Participants will be recruited from the Cardiac Rehabilitation Center at the Miriam Hospital (Providence, RI) and Lifespan Cardiovascular Institute, Lifespan Ambulatory Care Center (East Greenwich, RI). Patients deemed to meet initial inclusion criteria (i.e., HF diagnosis, aged \geq 55 years, no chart documentation of severe cognitive impairment or dementia, English-speaking) based on chart review will either be approached in the clinic or will be mailed a letter invitation to participate and contacted via phone one week later. Individuals who are approached in clinic will be asked to complete a "Consent to Contact" form. If patients do not respond to two telephone calls, they will not be telephoned again.

Screening

Patients will be asked to complete eligibility screening via telephone. Questions will be asked to check whether they meet the additional characteristics to be enrolled in the study (e.g., not participating in another medication monitoring protocol). They will also be asked to complete two questionnaires during the phone call: 1) Blessed Orientation Memory Concentration test (BOMC) to screen for significant cognitive impairment, and 2) risk for medication non-adherence as indicated referral to the pharmacist consultation service at cardiac rehab or endorsement of at least 1 non-adherence item on the Voils Extent of Adherence instrument (e.g. "no" on Question 1 or "yes" on Questions 2 or 3) or by being prescribed ten or more medications. Participants who score 10 or greater on the BOMC will not be eligible.

4 ASSESSMENT PROCEDURES

4.1 Baseline Assessments

- Demographics (self-reported)
- Charlson comorbidity index (completed via medical chart review).
- The Medication Management Instrument for Deficiencies in the Elderly
- Timeline follow-back medication adherence interview
- Medication Adherence Scale
- The Rapid Estimate of Adult Literacy in Medicine—Short Form
- Information--Motivation--Behavioral Skills Adherence Questionnaire (adapted for use in HF) administered for intervention tailoring purposes only (not scored)
- Memory Impairment Screen-Delayed.

Electronically Monitored Medication Adherence- Participants will also be asked to use a Tricella pillbox to monitor medications for 4 weeks. Participants will be asked to review their medication regimen with study staff. Prior to use, a study team member will demonstrate appropriate use of the pill boxes and will invite participates to practice opening and closing the containers. Study staffwill work with the participant to load each bin of the pill box bottle and provide detailed instructions for use. If participants take medications at two or three time points per day (e.g., morning and evening, or morning, noon, and evening), then the participant will be provided with a pillbox for account for each time period up to three.

Written instructions will be provided to all participants, including study staff contact information. Participants will be encouraged to contact staff in the event of any questions or concerns.

4.2 Follow-up call

One week following the baseline assessment and initiation of monitoring, study staff will call the participant to ask if there are any questions regarding use of the devices. Any emergent questions will be answered.

4.3 End of Treatment Assessment

- The Medication Management Instrument for Deficiencies in the Elderly will assess individual patient knowledge of their specific medication instructions.
- Timeline follow-back medication adherence interview
- Medication Adherence Scale
- Monitored Medication Adherence- pillbox collected for data transfer
- Study and Treatment Acceptability. Participants will be asked to take part in a brief (20-30 minutes) qualitative exit interview to gather participant reactions to the intervention and study procedures. These interviews will be completed by phone on the same day (immediately following or shortly thereafter) as the end-of-treatment visit. If needed due to participant availability, these interviews may be conducted within 1 week of the endof-treatment visit. Exit interviews will be audio recorded to facilitate transcription and note taking. Audio recordings will be stored on a secure server on the Lifespan network and will be deleted at the end of the study.

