5 INTERVENTION DELIVERY

Participants will complete a brief intervention in person immediately following the baseline assessment (about 60 minutes) and continued use of the study pillbox with the values affirmation prompt for the following 4 weeks. The session will include:

- 1. Participation in a values-affirmation exercise (i.e., Values card sort activity).
- 2. Working with the interventionist to devise a way to tangibly connect that value with medication-taking (i.e., placing a label with a word or picture of the value on a pill box or display next to the pill box).
- 3. Provision and review of a patient education workbook with recommendations for skills training activities to improve regimen management.

6 COMPENSATION

Participants will be compensated a total of \$70 in this research study. Specifically, they will receive \$30 in cash at the end of the first study visit, \$20 in cash at the end of the second study visit, and a \$20 gift card by mail after completing an exit interview via telephone.

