7 PRIMARY ENDPOINTS

- 1) Recruitment feasibility will be determined through examination of the percentage of eligible patients who enroll in the study.
- 2) Intervention feasibility will be calculated as the percentage of individuals who were enrolled and completed both the baseline assessment, intervention, monitoring period, and end-of-treatment assessment. Attrition will be assessed through examination of rates of dropout and reasons for non-completion. Feasibility of intervention procedures will be defined as achieving a retention rate of 80%.
- 3) Patient acceptance of the intervention will be determined by analysis of qualitative exit interview.

8 REFERENCES

Sobell, L. C., Cunningham, J. A., & Sobell, M. B. (1996). Recovery from alcohol problems with and without treatment: Prevalence in two population surveys. *American Journal of Public Health*, 86(7), 966–972.

Wu, J. R., Chung, M., Lennie, T. A., Hall, L. A., & Moser, D. K. (2008). Testing the psychometric properties of the Medication Adherence Scale in patients with heart failure. *Heart & Lung*, *37*(5), 334-343.

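### The exit interview is the only source for the acceptability endpoint, yet it is scheduled only around the end-of-treatment visit, so a participant who received the session but never has that visit has no planned interview.

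*Protocol*

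**What the plan says.** Protocol section 2 makes acceptability one of three primary endpoints: "Primary endpoints are feasibility of recruitment procedures, feasibility of intervention procedures, and acceptability". Section 7, item 3, bases patient acceptance on analysis of the exit interview. The SAP applies framework matrix analysis to the same interview. Neither document lists an acceptability scale or any other source.

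The interview appears in section 4.3, within the end-of-treatment assessment, as a "qualitative exit interview to gather participant reactions to the intervention and study procedures". Two sentences fix its timing, and both refer to the final visit:

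- Default: "These interviews will be completed by phone on the same day (immediately following or shortly thereafter) as the end-of-treatment visit".
- Extension: "If needed due to participant availability, these interviews may be conducted within 1 week of the endof-treatment visit".

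Exposure comes much earlier. Section 5 states: "Participants will complete a brief intervention in person immediately following the baseline assessment". Pillbox use then continues for 4 weeks.

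For people who do not finish, section 7, item 2, examines dropout rates and reasons for non-completion, under intervention feasibility. The SAP has no rule for missing interviews.

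**The concern.** A participant who has had the session and then withdraws, or never has the final visit, has views on the session, the pillbox and the study visits. All of these are within the interview's stated scope. The written schedule gives that person no interview, because both timing sentences need a visit to count from.

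If anyone is lost in this way, acceptability is assessed only among people who stayed to the end. Staying is itself part of another primary endpoint, so one endpoint would be judged in a group selected by success on another. If people who leave tend to like the intervention less, the acceptability result will be too favourable. In a study of 12, one or two absent interviews are a noticeable share of the evidence, and in a qualitative analysis one or two people may be the only ones to raise an objection.

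**Working it through.** The plan gives no figure to reproduce: there is no power calculation, dropout forecast or numeric criterion for acceptability. The check therefore has two parts: reading the schedule against the endpoint, and counting against the retention rule.

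**Reading.** Take a participant who completes baseline and the session, then leaves in week 2.

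- Section 5: the intervention session has been received.
- Section 4.3, default timing: there is no final visit, so no same-day call.
- Section 4.3, extension: there is no final visit, so no one-week window.
- Section 7, item 2: the person counts as a non-completer and a reason may be recorded, under feasibility.
- Section 7, item 3, and the SAP: the person contributes nothing to acceptability.

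A participant who stops using the pillbox but attends the final visit is already covered.

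**Counting.** Inputs: n = 12 (section 1, "12 older men and women with HF, ages 55 and older") and a retention criterion of 80% (section 7, item 2), where retention is the "percentage of individuals who were enrolled and completed both the baseline assessment, intervention, monitoring period, and end-of-treatment assessment".

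- Minimum completers: 0.80 × 12 = 9.6, so 10.
- 10/12 = 83.3% meets the criterion; 9/12 = 75.0% does not.
- Non-completers allowed with the criterion met: 12 − 10 = 2, and 2/12 = 16.7%.

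This is a ceiling on those who could miss the visit while retention is met. Some of the 2 might not have received the session, or might have attended the visit after failing the monitoring period. If completing the end-of-treatment assessment includes the interview, attenders who decline it fall within the same 2; if not, they add to it.

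**How likely is at least one loss? (illustration)** Assume each participant reaches the visit independently with probability p. Then P(at least one missing) = 1 − p^12, and P(at least one missing and criterion met) = P(10 or 11 of 12 attend).

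| p | At least one missing | At least one missing, criterion met | Expected number missing, 12(1 − p) |
|---|---|---|---|
| 0.70 | 98.6% | 23.9% | 3.6 |
| 0.80 | 93.1% | 49.0% | 2.4 |
| 0.90 | 71.8% | 60.7% | 1.2 |

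The 0.80 row borrows the protocol's criterion, which is not a forecast; 0.70 and 0.90 are assumptions.

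**What two missing interviews could hide (illustration).** The favourable counts below are assumed.

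- 10 interviewed, all favourable (100%): the share among all 12 lies between 10/12 = 83.3% and 12/12 = 100%.
- 10 interviewed, 8 favourable (80%): the share lies between 8/12 = 66.7% and 10/12 = 83.3%.
- Exactly 2 of 12 hold an objection and 2 are not interviewed: the objection is lost entirely with probability 1/C(12,2) = 1/66 = 1.5% if missing is unrelated to views, and with certainty if the two objectors are the two who leave.

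**The case against.** The strongest reply is that section 4.3 first says participants will be asked for an interview, without limiting this to attenders, and only then says when the call normally happens. On that reading the text is silent on an unusual case and sets no attenders-only rule. The interview is by phone, and section 6 pays a "gift card by mail after completing an exit interview via telephone", separately from the visit payment, so staff could call a leaver. This is fair, and the point is an omission, not a prohibition. But the interview is listed as part of the end-of-treatment assessment, no window exists for someone without that visit, and data collection for a primary endpoint should not depend on improvisation.

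Other replies stand in part:

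- A missed visit may be rescheduled, and the interview would then follow. The gap concerns only those who never have the visit, and some of them would refuse a call.
- Reasons for non-completion are examined, and every non-completer counts against retention, so leavers are not ignored overall. A recorded reason is much thinner than a 20 to 30 minute interview, however, and the plan does not bring it into the acceptability analysis.
- Terms for contact after withdrawal may be in consent pages not available for review. They could limit who may be called, but would not change the timing in section 4.3.
- The study is small and descriptive, and no declared success rule for acceptability would change. This limits the seriousness of the point. It does not remove it, because a few interviews are all the evidence this endpoint has.

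**Conclusion.** The concern holds. Acceptability rests on one interview whose only scheduled times depend on the end-of-treatment visit, so someone who received the session but never has that visit is left out unless staff go beyond the written schedule. From the documents' own figures, up to 2 of 12 participants (16.7%) could be unheard with the retention criterion met.

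Whether this biases the result depends on facts not in the documents. There is no bias if everyone has the visit or if leavers' views match those of attenders. If leavers are less favourable, the result is too favourable by an amount that cannot be computed. The attendance probabilities, favourable shares and lost-objection example all rest on assumed inputs and show only what is possible. This should be changed because the remedy is cheap and the endpoint is primary; it does not invalidate the study.

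**What to change.** **Protocol section 4.3:** add a sentence offering the same phone interview and $20 gift card to every participant who received the session, including those who withdraw or do not have the final visit, provided they agree to be contacted. For them, count the interview window from withdrawal or from baseline.

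**SAP:** report the number interviewed out of the number who received the session and out of the number enrolled, and count attenders who decline. Present non-completers' feedback and the reasons for non-completion beside the acceptability result, noting that early leavers can speak to the session and study procedures but not to the full 4 weeks.

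**Cost:** one sentence in the protocol and one or two in the SAP; whether consent wording also needs a change cannot be seen from the documents. At the retention benchmark, about two calls, 2 × 20 to 2 × 30 = 40 to 60 minutes in total, and 2 × $20 = $40, already within the planned $70 per person, plus transcription; more if dropout is higher. Some leavers will decline, so the gap shrinks but does not close. One or two such interviews support description only, not a comparison with completers.

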5 INTERVENTION DELIVERY

Participants will complete a brief intervention in person immediately following the baseline assessment (about 60 minutes) and continued use of the study pillbox with the values affirmation prompt for the following 4 weeks. The session will include:

- 1. Participation in a values-affirmation exercise (i.e., Values card sort activity).
- 2. Working with the interventionist to devise a way to tangibly connect that value with medication-taking (i.e., placing a label with a word or picture of the value on a pill box or display next to the pill box).
- 3. Provision and review of a patient education workbook with recommendations for skills training activities to improve regimen management.

6 COMPENSATION

Participants will be compensated a total of \$70 in this research study. Specifically, they will receive \$30 in cash at the end of the first study visit, \$20 in cash at the end of the second study visit, and a \$20 gift card by mail after completing an exit interview via telephone.

7 PRIMARY ENDPOINTS

- 1) Recruitment feasibility will be determined through examination of the percentage of eligible patients who enroll in the study.
- 2) Intervention feasibility will be calculated as the percentage of individuals who were enrolled and completed both the baseline assessment, intervention, monitoring period, and end-of-treatment assessment. Attrition will be assessed through examination of rates of dropout and reasons for non-completion. Feasibility of intervention procedures will be defined as achieving a retention rate of 80%.
- 3) Patient acceptance of the intervention will be determined by analysis of qualitative exit interview.

8 REFERENCES

Sobell, L. C., Cunningham, J. A., & Sobell, M. B. (1996). Recovery from alcohol problems with and without treatment: Prevalence in two population surveys. *American Journal of Public Health*, 86(7), 966–972.

Wu, J. R., Chung, M., Lennie, T. A., Hall, L. A., & Moser, D. K. (2008). Testing the psychometric properties of the Medication Adherence Scale in patients with heart failure. *Heart & Lung*, *37*(5), 334-343.

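### Is the 80% retention rule for intervention feasibility too loosely defined to be applied to 12 participants?

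*Protocol*

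**What the plan says.** Protocol section 7, item 2, takes as its numerator those enrolled who "completed both the baseline assessment, intervention, monitoring period, and end-of-treatment assessment". It then states the pass mark: "Feasibility of intervention procedures will be defined as achieving a retention rate of 80" percent. Between those two sentences it says that attrition will be examined through dropout rates and the reasons participants did not complete.

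The exit interview appears in several places:

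- Section 4.3, headed as the end-of-treatment assessment, lists it as a bullet: "Study and Treatment Acceptability. Participants will be asked to take part in a brief (20-30 minutes) qualitative exit interview". The same bullet allows a delay: "these interviews may be conducted within 1 week of the endof-treatment visit".
- Section 6 pays for it apart from the second visit, with a "gift card by mail after completing an exit interview via telephone".
- Section 7, item 3, makes it the data source for acceptability, which section 2 keeps separate: "Primary endpoints are feasibility of recruitment procedures, feasibility of intervention procedures, and acceptability".

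On monitoring, section 4.1 asks for four weeks of pillbox use. Section 5 describes "continued use of the study pillbox with the values affirmation prompt for the following 4 weeks", and section 4.3 ends the period with "Monitored Medication Adherence- pillbox collected for data transfer". No minimum amount of recorded use is given.

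The SAP plans frequencies and percentages for the primary endpoints and no inferential statistics. It does not repeat the 80% mark or define a completer.

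**The concern.** A pass/fail rule needs a numerator that two analysts would count in the same way, and here they might not. Through the heading of section 4.3, someone who had the session, kept the pillbox for four weeks and attended the final visit, but missed the telephone call, could be coded a non-completer. From sections 6 and 7, the same person could be coded a completer. Similarly, a pillbox returned with little recorded use could count as completed monitoring for one analyst and not for another.

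Only two participants can be lost before the rule fails, so the choice could decide whether the intervention is called feasible. If it were made after the counts were known, the verdict could follow the choice. In one direction, an intervention that all 12 finished could be labelled infeasible because of missed research calls. In the other, it could be labelled feasible although the boxes were hardly used.

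**Working it through.** **Inputs.** Planned enrolment n = 12 (section 1). Pass mark 80% of enrolled (section 7, item 2). The documents derive no sample size, power or error rate, so there is no calculated figure to reproduce.

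**Pass mark as a count.** Completers needed: r = 0.80 × n, rounded up.

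| Enrolled | 0.80 × n | Needed | Just passes | Just fails | Losses allowed |
|---|---|---|---|---|---|
| 12 | 9.6 | 10 | 10/12 = 83.3% | 9/12 = 75.0% | 2 |
| 11 | 8.8 | 9 | 9/11 = 81.8% | 8/11 = 72.7% | 2 |
| 10 | 8.0 | 8 | 8/10 = 80.0% | 7/10 = 70.0% | 2 |

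**When the interview matters.** Let V be the number who finish everything except possibly the interview, and m the number of those who miss it. With 12 enrolled, the two readings disagree only if V ≥ 10 and V − m ≤ 9:

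- V = 12: three missed calls (100% becomes 75.0%)
- V = 11: two missed calls (91.7% becomes 75.0%)
- V = 10: one missed call (83.3% becomes 75.0%)

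One participant decides the verdict only when V is exactly 10. The same counts hold for reclassifying who completed monitoring.

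**How often that could happen.** The documents give no rates, so these are assumptions. If each participant finishes everything else with probability 0.90, the exact binomial chance of at least 10 of 12 is 0.889. If a further 5%, 10% or 15% of those miss the interview, it falls to 0.753, 0.594 or 0.438. Completers with the interview are a subset of completers without it, so the chance that the readings disagree is the difference:

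- 5%: 0.889 − 0.753 = 0.136
- 10%: 0.889 − 0.594 = 0.295
- 15%: 0.889 − 0.438 = 0.451

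The gap is therefore not negligible if missed calls are common. Whether it is a defect depends on how open the text really is.

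**Interview: the text side by side.** For counting it: the heading of section 4.3. Against:

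- The bullet itself times the interview relative to the visit.
- Section 1 has each participant finish within four weeks, ending at the end-of-treatment assessment. A call up to a week after a visit that closes four weeks of monitoring would fall outside that limit.
- Section 6 pays for it as a separate step.
- Section 5 does not list it as intervention content.
- Section 7, item 3, assigns it to another endpoint.

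The second reading has more support.

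**Monitoring: the text side by side.** The period has a stated length and a stated end, collection of the box, and item 2 calls its criterion a retention rate. Remaining in the study until collection fits all three. A minimum-use rule would turn retention into adherence, in a sample that section 3.1 selects for being at risk of non-adherence.

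**The four parts together.** Section 5 places the session immediately after the baseline assessment, and the box is collected at the end-of-treatment assessment. On these readings the four parts come down to attending the first visit, staying in, and attending the last. That is what a retention rate ordinarily means, so the two sentences of item 2 agree.

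**The case for a change.** The strongest case for a change is that this is a primary endpoint with a binary rule, that two of its four parts lack a definition, and that the SAP supplies none. Descriptive analysis does not excuse an undefined numerator. If the sponsor already knows what it means, writing it down takes a few sentences. If it does not, the definition may be chosen with the results in view.

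Much of this stands. Neither document settles the two points expressly, the arithmetic is right, and the SAP is silent. Pillbox use after the first session could also go unexamined under a pure retention reading, since the SAP's exploratory analysis covers only self-report adherence. That limits what retention can show, but it is not a contradiction in the rule.

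The rest is weaker. The claim that the rule as written counts the interview rests on a heading, and item 2 never names the interview. If the heading did govern, the rule would be defined, and the complaint would become a preference about what belongs in the composite, which already includes two research assessments. The call is paid, normally made on the day of the final visit, and has a one-week fallback, so three missed calls among 12 full completers is a demanding scenario. A table of counts by part would refine the planned reporting of dropout and reasons for non-completion. It would not replace a faulty method.

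**Conclusion.** No change is needed. This is missing detail that an analyst can fill sensibly from the rest of the protocol: 80% applies to completion of the four parts among all enrolled (at least 10 of 12), the exit interview is reported under acceptability, and monitoring is complete when the participant remains until the pillbox is collected. A one- or two-sentence clarification before data transfer would be reasonable but optional.

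The possible effect is limited to switching a feasibility label between 83.3% or more and 75.0% or less, and a single participant can do so only at 10 versus 9. No estimate, test or error rate is involved, and the documents tie no stated decision to the label beyond the feasibility hypothesis itself.

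The conclusion rests on two assumptions. The first is that retention rate means the four-part percentage, which is the natural reading though not stated outright. The second is that the reasons for non-completion are reported as planned, in enough detail to show whether a participant missed only the interview. If so, a reader can recount under the other reading.
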